5.5 EXPLORATORY EFFICACY ANALYSIS

Some exploratory efficacy analyses will be performed on the FAS population, if not otherwise specified. Patients in Cohort B will be analyzed according to the treatment as it was assigned during efficacy analysis of the parent study. Analysis will be presented over time by cohort and treatment group as defined in Section 5.1.1. Baseline is defined as the last assessment prior to treatment on Day 1 of OLE study.

No intercurrent event will be considered in the exploratory endpoint analysis (with the exception of the time to event exploratory endpoints) and no imputation of the missing data is forecasted.

Patient-Reported Outcomes (PRO)

Summary statistics (number of patients, mean, standard deviation, median, minimum, maximum) on observed values and their change from baseline for patient-reported outcomes (PRO) efficacy endpoints (UCSD-SOBQ, SGRQ [individual domains and total score], and EuroQol 5-Dimension, 5-Level Questionnaire [EQ-5D-5L] index-based, and visual analog scale scores) will be presented for the PRO analysis population over time by cohort and treatment group as defined in Section 5.1.1.

Change-from-Baseline Exploratory Endpoints: HRCT

In Cohort B patients, summary statistics (number of patients, mean, standard deviation, median, minimum, maximum) on the raw values at each visit and the change from baseline to each visit through Week 52 and Week 104 will be computed for the quantitative HRCT imaging analysis parameters by treatment group as defined in Section 5.1.1 for Cohort B.

Acute Exacerbation of IPF Endpoints

Summary statistics for continuous variables will be prepared by cohort and treatment group (as defined in Section 5.1.1) for the total number and rate (per year) of acute or suspected exacerbations during the OLE period.

The number and proportion of patients with at least one acute or suspected exacerbation during the OLE period, as determined by Adjudication Committee, will be tabulated by cohort and treatment group as defined in Section 5.1.1.

Healthcare Utilization Exploratory Endpoints

Summary statistics (number of patients, mean, standard deviation, median, minimum, maximum) on absolute values will be prepared for:

- Length of hospital stay in days for respiratory-related hospitalizations;
- Total time in intensive care units in days due to respiratory causes;
- Unscheduled outpatient clinic/urgent care/emergency room utilization related to respiratory events.

Statistics will be presented over time by cohort and treatment group as defined in Section 5.1.1.

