3.3.3 Rationale for Collection of Survival Data in Cohort C

Patients with IPF have a very poor prognosis despite the availability of pirfenidone and nintedanib. Median survival remains low, between 2–5 years (Jo et al. 2018). IPF is the primary cause of death for 60% of patients with IPF, with death commonly occurring after an acute exacerbation of the disease. When an acute exacerbation of IPF is not the cause of death, other common causes include acute coronary syndromes, congestive heart failure, lung cancer, infection, and venous thromboembolic disease (Frankel and Schwarz 2009).

For patients who are unable or unwilling to continue with study treatment and/or assessments, the Sponsor will continue to collect their survival data unless patients withdraw consent to do so.

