5.3.2 Adverse Events

All verbatim (“investigator-reported”) AE terms will be assigned a standardized term (the “Preferred Term [PT]”) and a superclass term using the most current version of the Medical Dictionary for Regulatory Activities (MedDRA) thesaurus terms, and adverse event severity will be graded according to NCI CTCAE v5.0 scale. A by-patient AE data listing including onset study day, duration, PT, treatment, severity, relationship to treatment, treatment for AE, action taken, and outcome will be provided.

All AEs, SAEs, AEs leading to death, AESIs, and AEs leading to study treatment discontinuation that occur during or after the first dose of study treatment (i.e., treatment emergent adverse events [TEAEs]) will be summarized by PT and severity grade as appropriate. An exacerbation or worsening of a pre-existing condition will be considered treatment-emergent only if the most extreme intensity is greater than the intensity at baseline (i.e., the intensity for a given AE increases and its end date is on or after the date of the first dose in the OLE study). For events of varying severity, the highest grade will be used in the summaries. Listings of AEs, SAEs, and AESIs will also be produced. Any non-treatment emergent SAEs, will also be listed separately (SAE occurring in Cohorts A, B, and C before or after the AE reporting period, as described in Protocol Section 5.4 and Protocol Section 5.7).

Number of patients with AE, number of AEs, cumulative incidence of AE as well as the AE rate per 100 patient-years exposure (defined as the number of events/total duration in the study multiplied by 100) will be calculated, along with the corresponding 95% confidence intervals (CIs) for the patient-years' rates of the SOC (exact based on the Chi-square distribution [Ulm 1990]).

Summary tables of the following will be provided for each cohort and the treatment groups as described in Section 5.1.1, including, but not limited to:

- AEs and SAEs of any grade
- AEs by highest NCI CTCAE grade
- Severe AEs (NCI CTCAE Grade 3 or above)
- AEs leading to death
- AEs leading to study treatment discontinuation
- AEs leading to drug interruption
- AEs leading to withdrawal from study
- Treatment related AEs and SAEs
- AESIs defined as follows:

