 - Cases of potential drug-induced liver injury that include an elevated alanine aminotransferase (ALT) or aspartate aminotransferase (AST) in combination with either an elevated bilirubin or clinical jaundice, as defined by Hy's Law (see Protocol Section 5.4.)
 - Suspected transmission of an infectious agent by the study drug, as defined in Protocol Section 5.3.
 - Suspected IRR with NCI CTCAE Grade ≥ 2
 - Suspected anaphylactic or hypersensitivity reactions (all grades)
 - Acute or suspected exacerbation of IPF (all grades)

- Common AEs, i.e., those occurring in at least 5% of patients
- Suspected IRR (all grades)

Summaries of safety data by baseline concurrent anti-fibrotic therapy will be provided as appropriate.

Deaths and causes of death will be summarized and a listing of patients who died during the study will be provided.

Summaries of confirmed or suspected Coronavirus Disease 2019 (COVID-19) AEs and AEs associated with COVID-19 will also be provided.

A listing of all pregnancies will be presented.

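### The yearly exacerbation rate is planned as a continuous-variable summary, which implies a mean of per-patient rates; events over total patient-years should replace it.

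*SAP*

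**What the plan says.** SAP 5.5, under the acute exacerbation endpoints, states that "Summary statistics for continuous variables will be prepared by cohort and treatment group" for the "total number and rate (per year) of acute or suspected exacerbations during the OLE period". It defines neither the rate nor its denominator. Elsewhere in the same section the phrase is spelled out as "Summary statistics (number of patients, mean, standard deviation, median, minimum, maximum"). The section also states: "No intercurrent event will be considered in the exploratory endpoint analysis (with the exception of the time to event exploratory endpoints"). Death therefore has no handling in this analysis beyond ending the patient's follow-up. The next sentence of the SAP adds the number and proportion of patients with at least one adjudicated event. SAP 5.5.1 adds time to first event.

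For adverse events, SAP 5.3.2 uses a different form, an "AE rate per 100 patient-years exposure (defined as the number of events/total duration in the study multiplied by 100"). Its list of adverse events of special interest includes "Acute or suspected exacerbation of IPF (all grades").

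**The concern.** A pooled rate is one number per group and has no SD or median. Taken at its word, the SAP asks for one rate per patient, averaged with equal weight. A patient who has an event and is then followed only briefly contributes a very large value, because the event itself shortened the denominator.

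Follow-up for exacerbations can end soon after an event in two ways. One is death. The other is stopping treatment: Protocol Appendix 1 assesses exacerbations up to the study discontinuation visit, 8 weeks after the last dose, and Cohort C then collects survival only (Protocol Appendix 2).

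At stake is a reported yearly rate that may be too high, that rests on a few patients with short follow-up, and that does not measure the same thing as a rate per patient-year. The same report could then show two different exacerbation rates, one in the efficacy tables and one in the safety tables, with nothing to explain the gap.

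**Working it through.** The plan states no exacerbation rate, so there is no figure to reproduce. The check compares two estimators, with N_i the events and T_i the follow-up in years of patient i:

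- mean of patient rates = (1/n) × Σ(N_i / T_i)
- pooled rate = ΣN_i / ΣT_i

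**Leverage of one patient.** One event with follow-up ending at day 30 gives 365.25/30 = 12.2 per year. In a group of 300 this adds 12.2/300 = 0.041 to the mean. One event in a patient followed for a full year adds 1/300 = 0.003.

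**Illustration (invented data).** Take 100 patients: 90 with 2 years and no event, 5 with 2 years and one event, and 5 with one event and follow-up ending at 0.25 years.

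- Mean of patient rates = (90×0 + 5×0.5 + 5×4)/100 = 22.5/100 = 0.225 per year.
- Pooled rate = 10/(95×2 + 5×0.25) = 10/191.25 = 0.052 per year.
- The ratio is 4.3 and the median patient rate is 0. This case is chosen to show the mechanism, not the likely size.

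**Simulation.** None of these inputs comes from the documents: true rate 0.10 per year; 25% lost per year for other reasons; death after an exacerbation, when it occurs, uniform over 90 days; follow-up uniform on 0.1–1.5 or 1–4 years; minimum follow-up 1 day; 2,000,000 patients per setting. The ratio of the mean of patient rates to the pooled rate is:

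| Fatality after exacerbation | Follow-up 0.1–1.5 y | Follow-up 1–4 y |
|---|---|---|
| 0% | 1.00 | 1.00 |
| 5% | 1.05 | 1.09 |
| 10% | 1.11 | 1.19 |
| 30% | 1.33 | 1.53 |
| 50% | 1.54 | 1.89 |

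The pooled rate recovers 0.10 in every setting. True rates of 0.05 and 0.15 give nearly the same ratios. Unequal follow-up alone causes no bias, as the 0% row shows; the bias needs follow-up that depends on the event. Most patients have no event (about 93% and 85% at 50% fatality in the two follow-up settings), so the median is 0.

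**Sensitivity.** With a mean lag to death of one month, other-cause death of 0.05 per year and no other loss, and follow-up ranges from 0–1.5 to 2–6 years, the ratio is 1.50–1.95 at 30% fatality and 1.82–2.59 at 50%. At 0% it is again 1.00.

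**Precision.** With 300 patients, rate 0.10, 40% fatality and the inputs of the table above, the 5th–95th percentiles are about:

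| Follow-up | Mean of patient rates | Pooled rate |
|---|---|---|
| 0.1–1.5 y | 0.075–0.24 | 0.066–0.135 |
| 1–4 y | 0.11–0.27 | 0.077–0.124 |

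The standard error is about 0.06 for the mean of patient rates, against 0.022 and 0.014 for the pooled rate, so about 3 to 4 times as large.

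**The case against.** Five points can be made for the plan.

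1. **The per-patient formula is inferred.** This stands. The sponsor may have meant a pooled rate. The text would still need changing, because it gives no denominator and SAP 5.3.1 defines two candidates, treatment duration and study duration.
2. **A reader might infer from Protocol 3.3.3 that exacerbations often end in death.** The text does not say that. Its phrase "with death commonly occurring after an acute exacerbation of the disease" describes what tends to precede death in IPF, not the share of exacerbations that are fatal. Protocol 1.1 links exacerbations to a high risk of respiratory failure, also without a figure. The direction of the bias is clear if any such deaths occur, but its size cannot be taken from the documents.
3. **A pooled exacerbation rate is probably planned already**, through the adverse event rate in SAP 5.3.2. This largely stands, and it means a figure per patient-year may well be available. That rate would rest on investigator-reported events, and the SAP's confidence interval wording does not clearly reach each event of special interest.
4. **The yearly rate is not a listed endpoint.** SAP Table 1 lists time to first exacerbation, which SAP 5.5.1 analyses with explicit handling of IPF death. No tests are planned (SAP 2). This stands and lowers the priority.
5. **A reader might extend the criticism to healthcare utilization**, for instance to "Length of hospital stay in days for respiratory-related hospitalizations". The documents do not support that as a fault. Length of stay may be per admission, which needs no person-time, and SAP 5.5 presents these statistics over time.

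**Conclusion.** The point holds in limited form. Followed as written, SAP 5.5 leads to a mean of per-patient rates, which is a worse estimate of the group's exacerbation rate than events over patient-years, with an uninformative median of 0 beside it.

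The upward bias depends on how often, and how soon, death or the end of follow-up comes after an exacerbation. At a true rate of 0.10 per year it is nil at 0% fatality, 5–20% at fatalities of 5–10%, and 30–90% at fatalities of 30–50%; shorter lags and less other loss make it larger. All of these inputs are assumptions. It would go too far to say that the documents show the reported rate will be inflated by a particular amount.

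No hypothesis test or error rate is affected. The proportion with an event and the time-to-first-event analysis remain usable, although neither corrects the rate. Priority is low to moderate.

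**What to change.** In SAP 5.5, replace the continuous-variable summary of the yearly rate with total adjudicated acute or suspected exacerbations divided by total patient-years at risk, by cohort and treatment group, with a 95% CI. The events-over-total-duration form of SAP 5.3.2 can be reused.

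- State when time at risk starts and ends: for example, from Day 1 of the OLE to the earliest of death, the last contact at which exacerbations were assessed, or the data cut. Say how time after lung transplantation is treated.
- Say that the rate counts adjudicated events. At present only the sentence on the number and proportion of patients does so.
- If the safety tables also show a rate of investigator-reported exacerbations, add a footnote explaining the difference.
- Optionally, take the CI from a negative binomial or robust Poisson model with log follow-up time as offset, to allow for overdispersion.
- Keep the number and proportion of patients with an event and the time-to-first-event analysis as planned.

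The cost is a few lines of SAP text and one revised table shell. No new data are needed.

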5.5.1 Time-to-Event Exploratory Endpoints

The time-to-event exploratory endpoints are listed below:

- Time to first respiratory-related hospitalizations (defined as non-elective hospitalizations due to any respiratory cause, including acute exacerbations of IPF, or suspected acute exacerbations of IPF, as determined by Adjudication Committee)
- Time to first acute exacerbation of IPF, or suspected acute exacerbation of IPF, as determined by Adjudication Committee

Time-to-event will be measured in reference to baseline Day 1 of OLE study through the end of study or the time of the data-cut, whichever occurs first. For time to first respiratory-related hospitalizations and time to first acute exacerbation of IPF, patients not experiencing an event will be censored at the earliest of the last known alive day.

The strategy for the time-to-event endpoints is summarized below in [Table 5](#).

Table 5 Strategy for Addressing Intercurrent Events: Time-to-Event Exploratory Endpoints

Endpoint	Intercurrent Events and Strategy
Time to first respiratory-related hospitalizations (defined as non-elective hospitalizations due to any respiratory cause, including acute exacerbations of IPF, or suspected acute exacerbations of IPF, as determined by Adjudication Committee)	
Deaths due to IPF or other respiratory causes will be treated as disease progression and counted as event of interest (composite strategy)
 
Deaths due to other causes will be censored
 
Any patients who undergo lung transplantation will be censored at the date of the transplantation (hypothetical strategy)
 
Any patients who withdraw from treatment will be censored at the date of withdrawal (hypothetical strategy)

Time to first acute exacerbation of IPF, or suspected acute exacerbation of IPF, as determined by Adjudication Committee	
Deaths due to IPF will be treated as disease progression and counted as event of interest (composite strategy)
 
Deaths due to non-IPF causes will be censored
 
Any patients who undergo lung transplantation will be censored at the date of the transplantation (hypothetical strategy)
 
Any patient who withdraws from treatment will be censored at the date of withdrawal (hypothetical strategy)

IPF = idiopathic pulmonary fibrosis.

5.5.2 Additional Exploratory Efficacy Endpoints

Exploratory analyses may also be performed for additional measures (see below the list of additional exploratory efficacy endpoints) and subgroups of interest including concurrent use of IPF treatment and geographic region (see Section 5.6.6 for the complete list).

The additional exploratory efficacy endpoints are:

- Change from baseline in FVC% predicted, FVC (mL), by concurrent therapy stratum (i.e., with nintedanib treatment vs. with pirfenidone treatment vs. without pirfenidone or nintedanib treatment)
- Change from baseline in FVC% predicted, FVC (mL), by MUC5B status
- Change from baseline in 6MWD (m), by concurrent therapy stratum (i.e., with nintedanib treatment vs. with pirfenidone treatment vs. without pirfenidone or nintedanib treatment)

Summary statistics (number of patients, mean, standard deviation, median, minimum, maximum) on absolute values and their change from baseline.

5.6 OTHER ANALYSES

5.6.1 Summaries of Conduct of Study

Eligibility criteria deviations and other major protocol deviations will be summarized.

The impact of COVID-19 will be assessed by including major protocol deviations related to COVID-19 and by summarizing COVID-19-related intercurrent events by treatment arm.

Compliance analysis will be performed for the overall UCSD-SOBQ and SGRQ questionnaires. Compliance rates will be summarized by number and proportion of patients among those expected to complete the UCSD-SOBQ or SGRQ at each time point.

5.6.2 Summaries of Demographics and Baseline Characteristics

Unless otherwise specified, the baseline value for each variable will be considered for the assessment collected on baseline Day 1, prior to administration of first study drug during OLE period. For subjects in Cohort C directly recruited from Study WA42293, baseline will be Day 1, prior to administration of first study drug during double-blind period.

Demographic and baseline characteristics (including, but not limited to, age, sex, race/ethnicity, concomitant IPF medication use, comorbid illnesses, and pulmonary function) will be summarized overall for the FAS population and by cohort and treatment group (as defined in Section 5.1.1) using descriptive statistics as appropriate.

Compliance with study drug will be computed for each patient as the proportion of prescribed study drug actually taken for the safety population.

Proportions of patients taking each concomitant medication will be provided for the safety population.

Medical history will be summarized using summary statistics, reporting the proportion of patients with at least one medical condition and the total number of medical conditions based on the safety population.

5.6.3 Pharmacokinetic Analyses

The pharmacokinetic (PK)-evaluable population will consist of patients from Cohort A and Cohort B with sufficient data to determine plasma concentrations of zinpentraxin alfa at specified timepoints, unless major protocol deviations or unavailability of information (e.g., exact blood sampling time) occurred which may interfere with PK evaluation, with patients grouped according to treatment received.

Individual and mean plasma zinpentraxin alfa concentration versus time data will be listed and summarized (mean, standard deviation, coefficient of variation mean,

geometric mean, coefficient of variation geometric mean, median, minimum, and maximum).

The PK parameters for zinpentraxin alfa in plasma will be estimated as appropriate for each subject profile by non-compartmental analysis methods using Phoenix WinNonlin software (v8.3 or later, Certara USA, Inc.). Plasma PK parameters definitions are as below:

- C_{max} : maximum observed concentration
- T_{max} : time to maximum observed concentration
- AUC_{0-t} : area under the concentration-time curve from hour 0 to the last measurable concentration, calculated using the linear trapezoidal rule for increasing concentrations and the logarithmic rule for decreasing concentrations
- $AUC_{0-\infty}$: area under the concentration-time curve extrapolated to infinity, calculated using the formula:

$$AUC_{0-\infty} = AUC_{0-t} + C_t/\lambda_z$$

where C_t is the last measurable concentration and λ_z is the terminal elimination rate constant

- $\%AUC_{extrap}$: percentage of area under the concentration-time curve that is due to extrapolation from the last measurable concentration to infinity
- λ_z : terminal elimination rate constant, where λ_z is the magnitude of the slope of the linear regression of the log concentration versus time profile during the terminal phase
- $t_{1/2}$: terminal elimination half-life (whenever possible), where $t_{1/2} = (\ln 2)/\lambda_z$
- CL: systemic clearance
- V: volume of distribution

Other parameters may be added as appropriate. PK parameters analysis will use actual times as recorded on the eCRF.

Estimates for PK parameters will be listed and summarized (mean, standard deviation, coefficient of variation mean, geometric mean, coefficient of variation geometric mean, median, minimum, and maximum).

Additional exploratory PK analyses will be conducted as appropriate. Exploratory PK analyses to evaluate potential relationships between drug exposure and the efficacy and safety of zinpentraxin alfa might be described in a separate document and presented in a separate report.

5.6.4 Biomarker Analyses

Biomarkers will be assessed at baseline and subsequent timepoints following administration of zinpentraxin alfa (both Cohort A and Cohort B). Biomarkers will be

presented as absolute value over time and/or percent change relative to baseline over time. Biomarker levels at baseline or over time may be compared with efficacy or safety measurements to assess prognostic or predictive properties.

Descriptive or summary statistics will be used to describe biomarker assessments.

Exploratory biomarker analyses will be performed to identify and/or evaluate biomarkers in the context of drug activity, efficacy, PK, safety, and/or immunogenicity endpoints.

5.6.5 Immunogenicity Analyses

The following summaries will be provided for both Cohort A and Cohort B (only for patients who enrolled into the Study WA42293 prior to 1 June 2022) by the treatment group as defined in Section 5.1.1:

- Numbers and proportions of ADA-positive patients and ADA-negative patients at baseline (baseline prevalence) and after drug administration (post-baseline incidence)
- Number and percent of patients with at least one treatment-induced ADA
- Drug concentration at ADA collection timepoints

A by-patient listing of ADA status will be provided.

When determining post-baseline incidence, patients are considered to be ADA positive; if they are ADA negative or have missing data at baseline but develop an ADA response following study drug exposure (treatment-induced ADA response), or if they are ADA positive at baseline and the titer of one or more post-baseline samples is at least 0.60 titer unit greater than the titer of the baseline sample (treatment-enhanced ADA response). Patients are considered to be ADA negative if they are ADA negative or have missing data at baseline and all post-baseline samples are negative, or if they are ADA positive at baseline but do not have any post-baseline samples with a titer that is at least 0.60 titer unit greater than the titer of the baseline sample (treatment unaffected).

The relationship between ADA status and safety, efficacy, and pharmacokinetics may be analyzed and reported via descriptive statistics.

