1.3.1 Benefit–Risk Assessment

PRM-151, a recombinant form of an endogenous human protein, was generally well tolerated in nonclinical toxicity studies and in Phase I and II clinical studies. Clinically and statistically significant positive effects with PRM-151 were observed in the Phase II IPF Study PRM-151-202, both for change in FVC (% predicted) and 6MWD through 28 weeks of treatment. Based on encouraging Phase I and II data in patients with IPF, PRM-151 has the potential to be a well-tolerated, disease modifying treatment for a broad spectrum of fibrotic diseases, including IPF.

In the Phase II study (n=116), PRM-151 was generally well tolerated through at least 6 months of treatment as evidenced by the following:

- None of the serious adverse events (SAEs) reported during the study were considered related to the study treatment.
- Treatment-emergent adverse events (TEAE; serious and non-serious) leading to temporary discontinuation of study treatment were more common in the PRM-151 group than the placebo group overall (6 patients [7.8%] and 1 patient [2.6%], respectively), but these events were distributed across a range of body systems with no single preferred term reported in more than 1 patient and did not appear to indicate a safety risk for PRM-151.
- The most common adverse event (AE) assessed as possibly or probably related to study treatment was fatigue (16 events in 9 patients from the PRM-151 group [11.7%] and 3 events in 3 patients from the placebo group [7.7%]).
- Adverse events of cough with possible or probable relationship to study treatment were reported in 7 patients from the PRM-151 group (9.1%; seven events). No

patient from the placebo group was reported with possibly or probably related cough AEs.

- Four infusion-related reactions (IRRs) occurred in 3 patients: 2 patients in the PRM-151 group (2.6%), and 1 patient in the placebo group (2.6%). One patient in the PRM-151 group experienced dizziness and another experienced a hypertensive crisis event; 1 patient in the placebo group experienced 2 hypertensive crisis events. There was no difference between treatment arms in the nature or frequency of IRRs. None of the IRR events were deemed serious. There were no IRR events among the 7 patients with anti-drug antibodies (ADAs [6 patients in the PRM-151 group; 1 patient in the placebo group]) through Week 28.

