5.3.7 Other Safety Endpoints

Summaries of safety data by ADA status will be provided as appropriate. See Section 5.6.5 for more details on ADA status.

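### For previously treated patients, the SAP's only ADA-status rule labels stable antibody carried over from the parent study as ADA negative, which puts antibody carriers in the comparator

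*SAP*

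**What the plan says.** SAP 5.6.5 gives one rule for ADA status. It opens "When determining post-baseline incidence, patients are considered to be ADA positive", so it is written for incidence. There are two routes to positive. One is treatment-induced: patients qualify "if they are ADA negative or have missing data at baseline but develop an ADA response following study drug exposure". The other is treatment-enhanced: positive at baseline with a later titer at least 0.60 unit higher. Patients are negative, under the label treatment unaffected, "if they are ADA positive at baseline but do not have any post-baseline samples with a titer" showing such a rise.

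Section 5.6.5 names no ADA-specific baseline. The default in SAP 5.6.2 is the Day 1 assessment, "prior to administration of first study drug during OLE period". Protocol Appendices 3 and 4 schedule a pre-dose ADA sample on that day.

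SAP 5.3.7 states "Summaries of safety data by ADA status will be provided as appropriate" and refers to 5.6.5 for what ADA status means. Section 5.6.5 adds that the relationship of ADA status to safety, efficacy and PK may be described, again without a second definition. It also plans a table of baseline prevalence, drug concentrations at ADA sampling times, and a by-patient listing of ADA status.

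**The concern.** A rule of this kind suits patients who have never had the drug: antibody present at baseline then pre-dates treatment, and a stable titer means that treatment did nothing to it. That reasoning fails for patients who reach OLE Day 1 already treated. Under SAP 1.2 and 1.2.1 these are all of Cohort A and the former zinpentraxin alfa arm of Cohort B. Their baseline antibody may be drug-induced, and calling it treatment unaffected can be untrue.

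For incidence within the OLE this is a matter of labelling. For comparisons by ADA status it changes who is compared with whom. Persistent carriers are a key group if antibody affects infusion reactions, exposure or efficacy, and they sit with the antibody-free patients. Protocol 1.3.1 names loss of efficacy and cross-reaction with the endogenous protein as possible consequences of ADA, and Protocol 2.5 makes the relationship an exploratory objective.

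The label also means different things in the two Cohort B arms: positive after first exposure in former-placebo patients, but new or boosted after earlier exposure in former-active patients. The planned all-patients group (SAP 5.1.1) pools the two.

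**Working it through.** **Step 1. Apply the rule to each type of patient, with OLE Day 1 as baseline.**

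| Patient | Label under SAP 5.6.5 |
|---|---|
| (a) Previously treated, positive at OLE Day 1, stable titer | ADA negative |
| (b) As (a), but titer rises by at least 0.60 | ADA positive (enhanced) |
| (c) As (a), but Day 1 sample missing and a later sample positive | Most naturally ADA positive (induced) |
| (d) Negative at OLE Day 1, later positive, in either former arm | ADA positive (induced) |

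Only (a) is misfiled for the status comparisons. Patients (a) and (c) may have the same antibody history; their labels differ because of one missing sample.

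**Step 2. Inputs.** The documents give no expected ADA count for this study, so there is no planned figure to reproduce. Protocol 1.3.1 reports "7 patients with anti-drug antibodies" through Week 28 of the Phase II study: 6 on active drug and 1 on placebo. In the same section, 6 active patients are 7.8% and 1 placebo patient is 2.6% of a total of 116. This gives arms of 77 and 39 (77 + 39 = 116).

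- Active: 6/77 = 7.8%.
- Placebo: 1/39 = 2.6%, which suggests that some of the 7.8% may be background.

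**Step 3. Upper illustration, former-active patients.** Assumptions, not in the documents: all of the 7.8% persists to OLE Day 1, no titer rises by 0.60, and a further 2% to 8% of patients become newly positive.

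- Misfiled share of carriers = p/(p + new), with p = 0.078.
- At 2% new: 0.078/0.098 = 80%. At 3%: 72%. At 5%: 61%. At 8%: 0.078/0.158 = 49%.
- Carriers as a share of the ADA-negative group: q = p/(1 - new), from 0.078/0.98 = 0.080 to 0.078/0.92 = 0.085.
- If carriers have 3 times the risk of non-carriers, the comparator risk is inflated by the factor 1 + 2q. The reported ratio is 3/(1 + 2q), which is 2.59 to 2.57.

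**Step 4. Let persistence and boosting vary.** Assumptions: 30-90% persistence, 0-50% of baseline-positives boosted, 0-4% late new ADA in former-active patients. Former-placebo patients have 2.6% background, and 7.8% of the remainder become positive on first exposure. Figures are per 100 patients in each former arm (equal arms assumed).

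- Former-active, worst case (90%, 0%, 0%): 7.0 carriers, 0 labelled positive, so 0% captured.
- Former-active, best case (30%, 50%, 4%): 2.3 positive at baseline, of whom 1.2 are boosted, plus 3.9 new. That is 5.1 labelled positive out of 6.2 carriers, or 81% captured.
- Former-placebo: 7.6 to 8.9 labelled positive out of 10.2.
- Both arms together: from (0 + 7.6)/(7.0 + 10.2) = 44% to (5.1 + 8.9)/(6.2 + 10.2) = 85%.
- With 30% persistence, no boosting and no new ADA, q = 0.023, and a true ratio of 3 is reported as 3/(1 + 0.046) = 2.87.

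**The case against.** The rule is introduced for incidence and is ordinary for that purpose. Carriers are not hidden: baseline prevalence is the first half of the immunogenicity endpoint, and the by-patient listing and the drug concentrations at ADA sampling times are planned regardless. ADA is also sampled at Grade 2 or higher infusion reactions and at suspected anaphylaxis or hypersensitivity (Protocol 5.1.4). The status comparisons are descriptive, some are optional, and no tests are planned. The attenuation is modest even in the upper illustration. The missing-baseline anomaly cannot be sized, because the sample is scheduled and no missing rate is given.

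All of this stands, and it limits the importance of the point. It does not remove it. Tabulating carriers at baseline does not take them out of the comparator, and a programmer following 5.3.7 to 5.6.5 finds only the incidence rule.

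A reader might infer that the rule empties the ADA-positive group, or that the group as a whole loses most of its members. The documents do not support that. Boosted antibody, new antibody and all drug-induced antibody in former-placebo patients stay positive. Only in the former-active arm could the group be empty, and only with no boosting and no new ADA.

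**Conclusion.** The point holds for previously exposed patients. With OLE Day 1 as baseline, persistent antibody at a stable titer is labelled ADA negative. This depletes the ADA-positive group and places carriers in the comparator for the descriptive safety, efficacy and PK comparisons.

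The size cannot be fixed. The 49-80% misfiled share and the fall in risk ratio from 3 to about 2.6 rest on full persistence, no boosting and 2-8% new ADA, and should be read as an upper illustration. With persistence and boosting varied, 0-81% of former-active carriers, and 44-85% of Cohort B carriers overall, would still be labelled positive. The documents give no ADA rate for WA42293, no persistence or boosting rate and no titer scale, and the Phase II figure covers 28 weeks only. The main cost is lost members in a positive group that is likely to be small, more than bias in the ratio. The change is worth making because it is cheap; it does not threaten the study's main conclusions.

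**What to change.** - Keep the 0.60 rule for incidence within the OLE.
- For every comparison by ADA status, in all cohorts and arms, class a patient as ADA positive if any OLE sample, including OLE baseline, is positive. Show patients who are positive at OLE baseline and treatment unaffected as their own category. Using one definition throughout, including former-placebo patients, keeps the Cohort B all-patients group coherent.
- Where comparable WA42293 ADA results are available, use the last parent-study sample when the OLE baseline is missing in a former-active patient. Add a supplementary incidence version with the pre-first-dose parent-study sample as baseline.

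The first two items need SAP wording and one derived variable from samples already scheduled. The third depends on assay comparability and on access to parent-study results: Protocol 4.5.3 describes transfer of WA42293 medical history and ongoing adverse events but does not mention ADA results, and it describes no such transfer from PRM-151-202. The downside is a small programming effort, and results for baseline-positive patients must be read together with the separate category.
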